We are proposing the first in man use of this technology for placement of the glenoid component in anatomic total shoulder arthroplasty. We will use, as we have for our completed PSI clinical trial and currently active IRI study, post-operative 3D CT Scanning to precisely define the location of the implant as compared to pre-operative plan. We propose to compare the accuracy of implant placement using the RTI - SmartBone technology to the use of IRI and PSI groups as well as the two control groups from these trials. Specifically we are proposing a non-randomized clinical case series. Patients enrolled in this study will be operated on by surgeons involved in the pre-clinical trial and the ongoing IRI study. In all enrolled RTI cases the surgeon will have full control to define the optimal position of the guide pin and the final implant. The surgeon can default to standard of care technology in any case in which the RTI technology cannot be used or results in a guide pin position that in his view is not consistent with the pre-operative plan. Therefore the surgeon is in full control of all intraoperative decision making and execution of the procedure.

In the 60 patients treated in the PSI and IRI study there has not been the need to abort the use of the novel instrumentation, nor has there been a complication during or after surgery relating to the technology. Moreover the objective data of post-operative implant position has proven the PSI and IRI technology to be better than control groups. It is for these reasons that we do not propose to do a randomized clinical trial.

Measurement of Implant Position

Post operatively we will obtain a CT scan with metal artifact reduction technology within the first few weeks after surgery and will generally obtain this scan prior to discharge from the hospital. A second CT scan will be obtained at two years after surgery. We have used these methods of 3D CT imaging to determine implant position in several prior studies. We have defined the accuracy of these measurements using first generation techniques to be within 1 millimeter and 3 degrees. We anticipate that the accuracy of these second generation imaging techniques will be improved from our earlier work.

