properly determine the quality of the bone stock surrounding the implant. Further correlating this with RSA and 3D CT imaging of implant movement, we can fully develop cause and effect of bone quality on glenoid component loosening.

The participating surgeons will be [name] and [name]. Patients may have surgery at either Cleveland Clinic main campus or at Euclid Hospital. If the procedure is performed at Euclid Hospital, post-operative CT scan and RSA (if chosen), will need to be taken at main campus within 3 weeks. The patient will be made aware of this at the time of enrollment and consent.

Inclusion/Exclusion Criteria:

To be eligible for inclusion, a primary anatomic total shoulder arthroplasty must be indicated for the patient.

Outcome Measures:

By comparing computer generated pre-operative plan to post op component placement, we will be looking at three outcomes. First, the overall difference in component placement between standard of care instrumentation, intelligent reusable instrument (IRB#12-997), patient specific instruments (IRB #10-582) and real time instrumentation will be compared. Secondly, we will compare the placement between the technologies within and between surgeons. Thirdly, we will evaluate the difference in implant position between technologies based on severity of pathology. The quality of the bone core sampled will be correlated to the possible loosening of the implants.

Sample Size:

We expect to enroll 20 patients for this clinical case series. Data collected will be analyzed in association with the enrollees from IRB#12-997 and IRB#10-582.

Statistical Methods

Average deviations from plan for the RTI, IRI, and freehand groups will be compared using mixed-effects ANOVA methods. Random effects will be included to account for correlation between observations introduced as a consequence of multiple observations of deviation being taken on a particular surgeon. If significant differences are found, multiple comparisons based on the ANOVA model will be made to compare each pair of groups, and will use Holm's step-down procedure to control the family-wise error rate of the tests.

All analyses will be done using R software (version 3.0.0, Vienna, Austria). A significance level of 5% will be used for all testing.

Data Sheets

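### The overall technology comparison is non-randomised, but its stated model does not adjust for the pre-operative severity that the trial measures

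*Combined protocol and SAP*

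**What the plan says.** All references are to the combined protocol and SAP.

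- **Design** (Glenoid Instrumentation and Pre-operative planning): "Specifically we are proposing a non-randomized clinical case series". The comparators are the IRI and PSI groups and the control groups of those two trials. Sample Size adds: "Data collected will be analyzed in association with the enrollees from IRB#12-997 and IRB#10-582". The PSI study is complete; IRB#12-997 is described as ongoing.
- **Model** (Statistical Methods): "Average deviations from plan for the RTI, IRI, and freehand groups will be compared using mixed-effects ANOVA methods". For the clustering that arises from repeated cases by one surgeon, the section adds: "Random effects will be included to account for correlation between observations". Pairwise testing comes next: "If significant differences are found, multiple comparisons based on the ANOVA model will be made to compare each pair of groups", with Holm's procedure and a 5% level. No patient-level covariate, matching, weighting or stratification is named.
- **Eligibility**: "To be eligible for inclusion, a primary anatomic total shoulder arthroplasty must be indicated for the patient". Detailed Study Design adds requirements on CT coverage, slice thickness and scan quality.
- **Severity data** (Data Sheets): pre-operative glenoid version and inclination, their estimated pre-morbid values, and depth of bone loss.
- **Severity as an outcome** (Outcome Measures): "Thirdly, we will evaluate the difference in implant position between technologies based on severity of pathology". No model or severity measure is given for this third outcome.

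**The concern.** Nothing in the design makes the RTI patients alike in severity to the patients of the other two studies. The arthroplasty indication admits a wide range of glenoid deformity, and the CT requirements concern image quality. The surgeon random effect deals with clustering by operator, not with the mix of patients.

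Two conditions together would bias the group difference: severity differs between the groups, and severity affects deviation from plan. The difference would then be partly case mix, yet the plan would test it at 5% and it would be read as an effect of the instrument. The direction could favour or disfavour RTI. Leaving severity out of the stated model also means that any later adjustment could use measures chosen after the data are seen.

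**Working it through.** The plan gives no figure to reproduce: the sample size of 20 comes without an SD, effect size or power. The check therefore has two parts.

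**1. Reading.** Terms named in the model: technology group (fixed) and surgeon (random). Severity measures collected: version, inclination, pre-morbid estimates and depth of bone loss. Overlap: none. The third outcome asks whether the technology difference varies with severity. That is effect modification and leaves the first outcome, the overall difference, unadjusted.

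**2. Illustration.** From the documents: 20 RTI patients; three groups (RTI, IRI, freehand); overall test at 5%, then Holm over three pairs. Assumed: no true technology effect; IRI and freehand groups of 20 or 30 each; residual SD 3 degrees; 30% of RTI patients severe; the same severe share in both comparators; severe cases deviating on average 2 or 4 degrees more; no surgeon clustering. The documents give 60 patients for the PSI and IRI studies together, with no split by group.

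Spurious RTI minus IRI difference = gap × (severe share in RTI − severe share in IRI):

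- 2-degree gap, 30% vs 60%: 2 × (0.30 − 0.60) = −0.6 degrees
- 4-degree gap, 30% vs 60%: 4 × (0.30 − 0.60) = −1.2 degrees

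Standard error of that difference for 20 versus 20. The within-group variance is 9 + gap² × p(1 − p). With a 4-degree gap this is 9 + 16 × 0.21 = 12.36 in RTI and 9 + 16 × 0.24 = 12.84 in each comparator, pooled 12.68, SD 3.56. The SE is 3.56 × √(1/20 + 1/20) = 1.13 degrees. The −1.2 degree bias is thus about one standard error.

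Simulated RTI versus IRI false-positive rate under the planned overall test and Holm (20,000 runs per setting; comparator groups of 20 / 30):

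| Severe share in comparators | 2-degree gap | 4-degree gap |
|---|---|---|
| 30% (no imbalance) | 1.7 / 1.9% | 1.8 / 1.6% |
| 40% | 1.8 / 1.9% | 2.3 / 2.8% |
| 50% | 2.8 / 2.7% | 4.8 / 5.0% |
| 60% | 4.1 / 4.3% | 9.3 / 11.3% |

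The baseline is below 5% because the overall test and Holm share the error over three pairs. A separate repeat of the 60%, 4-degree setting (6,000 runs) gave 10.4 / 11.1%. The chance of any false RTI difference, against IRI or freehand, at 60% is 6.6 / 7.0% (2 degrees) and 14.6 / 16.7% (4 degrees), from about 3% without imbalance. With the severity indicator in the model, RTI versus IRI is 1.6 to 2.0% and any RTI difference 2.6 to 3.3%.

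**Form of the covariate.** That recovery occurs because the fitted covariate is the one that generated the data. A second simulation let deviation rise by 2 degrees per SD of absolute departure, with comparators 1.6 times as spread (groups of 20/30/30, 5,000 runs):

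| Model | False-positive rate, RTI vs IRI | Bias (degrees) |
|---|---|---|
| Unadjusted | 7.3% | −0.98 |
| Signed linear covariate | 6.3% | −0.94 |
| Absolute covariate | 1.7% | 0 |

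If departure in either direction makes a case harder, a signed covariate leaves almost all the bias in place.

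**The case against.** The strongest reply is that severity has not been forgotten. The plan ranks none of its three outcomes, the third concerns severity, the endpoint is deviation from each patient's own plan, and the RTI surgeons also took part in the IRI study. A reader might infer from the model alone that the plan ignores severity; the third outcome shows that it does not. What remains is that this outcome has no model and does not adjust the first. Measuring against each patient's own plan removes differences in target, not in how hard the target is to reach. Shared surgeons do not equalise patients, and the documents support the overlap only for the IRI study.

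The second reply is that the harm is conjectural, and this stands. A reader might infer that the RTI comparison is biased, or biased in RTI's favour. The documents report neither severity by group nor a readable relation between severity and deviation (the figures are not available here). In the table, clear inflation for RTI versus IRI needs a doubled severe share and a 4-degree gap. Larger rates could be produced with 60 patients per comparator group, but 60 is the total stated for both earlier studies. A single ungated test at 5% would also give larger rates, but that is not the planned procedure.

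The third reply is that the simulated outcome is a simplification. Data Sheets lists positions in millimetres as well as version and inclination, and the plan does not say whether average deviations are signed or absolute. If signed, severity could widen the spread without moving the mean. This also stands, and the illustration is conditional on it.

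**Conclusion.** The concern holds as a gap in the analysis that should be closed: a non-randomised comparison with patients of two other studies, tested formally, with no severity term although severity is measured. It is not a demonstration of bias, whose size and direction are unknown and which may be nil. Under the assumed inputs (comparator groups of 20 to 30, 30% versus 60% severe, residual SD 3 degrees, mean deviation rising with severity), the RTI versus IRI false-positive rate goes from about 2% to about 4% with a 2-degree gap, or 9 to 11% with a 4-degree gap. Adjustment brings it back to about 2% only if the covariate matches the way severity acts.

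A reader might also infer that adjustment would make the groups comparable. It would cover measured severity only. Patient Enrollment and Detailed Study Design exclude patients in whom RTI is not used, or the pin is changed without it, and they have no post-operative imaging. If those are the harder cases, the RTI group is selected in a way that a covariate does not correct. Confidence is medium, because the two conditions for bias cannot be checked from the documents.

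**What to change.** In Statistical Methods, add one or two pre-specified severity covariates from Data Sheets as fixed effects in the overall technology comparison. A reasonable default is depth of glenoid bone loss and the absolute (unsigned) departure of version from its estimated pre-morbid value. Keep the surgeon random effect, the overall test and Holm. Fix the covariates and their form before the data are analysed. Tabulate the severity measures by group, and report the unadjusted result as a sensitivity analysis. If the measures cannot be obtained for a comparator group, label that comparison as unadjusted.

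A model for the third outcome, and a statement of the surgeon terms for the second, would be useful but are optional and separate from this point.

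The cost is a few sentences, one or two degrees of freedom, and a slightly larger standard error if severity turns out to be irrelevant. In simulation with three covariates that increase was about 1 to 7%; if the three together contributed an SD of about 2 degrees, the standard error instead fell by about 10 to 14%. The practical burden is retrieving the same measures from the planning CTs of the other two studies. The documents do not state whether these are available.

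### Pairwise comparisons depend on a significant three-group ANOVA, no confidence interval is planned, and PSI is left out, so the stated RTI comparisons may end without a usable result

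*Combined protocol and SAP*

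**What the plan says.** The aim is comparative. Under Glenoid Instrumentation and Pre-operative planning: "We propose to compare the accuracy of implant placement using the RTI - SmartBone technology to the use of IRI and PSI groups", together with the control groups of the two earlier trials. Outcome Measures repeats this. Its first outcome lists standard-of-care instrumentation and IRI, and ends "patient specific instruments (IRB #10-582) and real time instrumentation will be compared".

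Statistical Methods is narrower. The model covers three groups: "Average deviations from plan for the RTI, IRI, and freehand groups will be compared using mixed-effects ANOVA methods". Pairwise work is conditional: "If significant differences are found, multiple comparisons based on the ANOVA model will be made to compare each pair of groups", and it "will use Holm's step-down procedure to control the family-wise error rate of the tests". Finally, "A significance level of 5% will be used for all testing".

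Sample Size says "We expect to enroll 20 patients for this clinical case series", with no power, SD, effect size or margin. The data are to be analysed with those of the two earlier studies, but no section gives the size of any comparator group. No section plans a confidence interval, promises an estimated difference between groups, or says how a non-significant result is to be read.

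**The concern.** RTI is described in the Overall Summary as joining features of PSI to the IRI technology, and both of those are said to have beaten their controls already. How RTI compares with IRI and PSI is therefore at least as informative as whether it beats freehand placement. The plan handles that question poorly in three ways:

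- **ANOVA not significant.** The stated rule stops there and no RTI v IRI contrast is made.
- **ANOVA significant because freehand differs.** RTI v IRI is tested, but may be left as a non-significant p-value with no interval to show which differences remain possible.
- **RTI v PSI.** It is not analysed under either outcome, because PSI is not among the model's groups.

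At stake is what this first-in-man series can report. A reader given only a non-significant RTI v IRI result could take it to mean similar accuracy when a material loss has not been excluded.

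**Working it through.** There is no sample-size calculation to reproduce; 20 is an enrolment expectation.

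**Inputs**
- RTI: n = 20 (Sample Size). Two-sided alpha 0.05; the plan gives 5% without stating sidedness.
- IRI: n not given; assumed 20 to 40. The only clues are 22 beaded patients so far in the IRI study (Measurement of Implant Position) and 60 patients across the PSI and IRI studies (Glenoid Instrumentation and Pre-operative planning), with no clear split between device and control.
- Freehand: n not given; assumed 20 to 60.
- SD: not given. Results are in SD units and cannot be converted to degrees or millimetres.
- Surgeon random effects are ignored.

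**Step 1: RTI v IRI alone, before Holm.** SE = sqrt(1/20 + 1/n). Half-width = t(0.975, 18 + n) × SE. Power comes from the noncentral t with noncentrality 0.5/SE. The difference detectable with 80% power is approximately (1.960 + 0.842) × SE.

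| IRI n | SE | t | CI half-width (SD) | Power at 0.5 SD | Detectable at 80% (SD) |
|---|---|---|---|---|---|
| 20 | 0.316 | 2.024 | 0.64 | 33.8% | 0.89 |
| 22 | 0.309 | 2.021 | 0.62 | 35.2% | 0.87 |
| 30 | 0.289 | 2.011 | 0.58 | 39.7% | 0.81 |
| 40 | 0.274 | 2.002 | 0.55 | 43.5% | 0.77 |

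A true difference of half an SD would be missed more often than found across the whole range.

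**Step 2: how often the ANOVA condition is met.** Suppose RTI equals IRI and freehand is worse by d SD. The noncentrality is d² × n_F × (N − n_F)/N, where n_F is the freehand size and N the total. For sizes 20/20/20 (RTI/IRI/freehand) and d = 0.5, this is 0.25 × 20 × 40/60 = 3.33, giving 34%. For 20/30/60 it is 0.25 × 60 × 50/110 = 6.82, giving 63%.

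| Freehand worse by | ANOVA significant |
|---|---|
| 0.5 SD | 34% to 63% |
| 0.75 SD | 66% to 94% |
| 1.0 SD | 90% to over 99% |

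**Step 3: the whole rule, by simulation** (8,000 runs per scenario; sizes 20/22/20 and 20/22/30). With RTI equal to IRI, freehand worse by 0.75 to 1.0 SD and the ANOVA significant, RTI v IRI is non-significant in about 96% of runs. With RTI truly worse than IRI by 0.5 SD, and freehand worse than IRI by 0.5 to 1.0 SD, the full rule declares RTI different from IRI in only 22% to 28% of runs. A non-significant RTI v IRI result is therefore expected both when the two are equal and, most of the time, when RTI is half an SD worse.

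**Step 4: whether the ANOVA condition is needed.** Holm's procedure controls the family-wise error rate by itself. The preliminary F test is not needed for that purpose, and it can suppress the contrasts of interest.

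**The case against.** The strongest reply is that this is a 20-patient case series with no equivalence or non-inferiority aim. The documents speak only of comparing groups, and nowhere say that a non-significant result will be called equal accuracy. The plan does not forbid estimates, and group averages are what the ANOVA analyses. Freehand is in the model: PSI and IRI are said to have beaten control, and RTI beat standard of care in sawbones, so the ANOVA may well be significant.

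Much of this stands, and it rules out several stronger readings:

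- A reader might infer that RTI matching IRI and PSI is the expected result. The documents give no RTI v IRI or RTI v PSI data and predict nothing of the kind.
- A reader might infer that RTI v PSI would come out as non-significant. As written it would not be tested at all.
- A reader might infer that the plan will normally yield no RTI v IRI contrast. Step 2 shows that this depends on freehand: it is a substantial risk if freehand is about 0.5 SD worse and a small one at 1.0 SD.
- A reader might take "within 1 millimeter and 3 degrees" as a ready-made margin. Measurement of Implant Position gives it as the accuracy of first-generation imaging and expects the newer methods to do better. Measurement accuracy is not a tolerable difference between group means.

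Even a well-chosen margin would not by itself support a claim of similar accuracy. The comparison is non-randomised, and under Patient Enrollment and Detailed Study Design, patients in whom RTI was not used, or the pin was changed without it, are excluded and receive no post-operative CT.

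The reply does not remove the written condition on pairwise comparisons, the missing intervals or the absence of PSI.

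**Conclusion.** The point holds as a defect in the analysis wording. The plan can end with no RTI v IRI contrast, or with only a non-significant p-value for it, and it provides no RTI v PSI analysis although that comparison is stated twice as an aim. Under the assumed sizes, power for a 0.5 SD difference between RTI and IRI is 33.8% to 43.5% before Holm and 22% to 28% under the full rule in the scenarios simulated. Non-significance would say little about similarity.

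The missing text, the ANOVA condition and the PSI omission are read directly from the documents. The magnitudes rest on assumed comparator sizes, a common SD and no surgeon effect. The documents do not support saying that the sponsor intends to claim equivalence, or that such a claim is the likely outcome.

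**What to change.** 1. Add PSI to the model, so that it matches Outcome Measures.
2. Report RTI v IRI, RTI v PSI and RTI v freehand as model-based mean differences with 95% CIs, whatever the ANOVA result.
3. Keep Holm for the tests, and state which comparisons form the family. Four groups give six pairs instead of three, so the first Holm threshold falls from 0.05/3 = 0.0167 to 0.05/6 = 0.0083 if all pairs are kept. State too that the intervals are for estimation and are not Holm-adjusted.
4. State that a non-significant result will not be reported as equal accuracy.
5. Do not adopt the 1 mm and 3 degree figures as a margin. If the sponsor wishes to claim similar accuracy, it should justify a margin before the data are seen, and qualify the claim by the non-randomised comparison and the exclusion of patients in whom RTI was abandoned.

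The cost is slightly more analysis and somewhat stricter tests if all six pairs stay in the family. No extra patients, visits or imaging are needed for the RTI series. The sponsor gives up describing a non-significant result as equivalence.

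### With the three groups named in Statistical Methods, Holm's correction after a significant ANOVA is surplus and costs about 5 to 8 points of power; with four or more groups it can be replaced but not simply dropped

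*Combined protocol and SAP*

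**What the plan says.** Statistical Methods sets out the analysis in two stages.

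- **Overall test:** "Average deviations from plan for the RTI, IRI, and freehand groups will be compared using mixed-effects ANOVA methods".
- **Pair tests:** only after a significant overall result, "multiple comparisons based on the ANOVA model will be made to compare each pair of groups". These "will use Holm's step-down procedure to control the family-wise error rate of the tests".
- **Level:** "A significance level of 5% will be used for all testing".

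The list of groups differs between sections. Statistical Methods has three. The first outcome under Outcome Measures covers standard of care and IRI as well, and says that "patient specific instruments (IRB #10-582) and real time instrumentation will be compared", which makes four. The design text under Glenoid Instrumentation and Pre-operative planning names IRI, PSI and the two control groups of those trials as comparators, which makes up to five with RTI.

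RTI enrols 20 patients (Detailed Study Design; Sample Size). No effect size, SD, power or primary pair is given.

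**The concern.** Two safeguards against false positives are placed one on the other: a gate ("If significant differences are found") and then a correction over all pairs. With three groups the gate already does the work of the correction. The second layer then lowers the chance of detecting an RTI difference and gives no protection that the first lacks. With only 20 RTI patients, power that can be recovered without recruiting anyone is worth having.

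Whether the second layer is surplus depends on how many groups are analysed, and the document does not settle that.

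**Working it through.** **Inputs from the document.** Level 5% (two-sided assumed for pair tests); three groups, so 3 pairs; four groups under the first outcome, so 6 pairs; 20 RTI patients.

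**Inputs assumed.** Comparator groups of 20 to 30, differences (d) of 0.5 to 1.0 SD, equal SD, normal data, no surgeon effect. There is no stated power to reproduce.

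**1. Logic for three groups.** If any two of the three pairwise nulls hold, all three group means are equal, so every intersection of pairwise nulls is the complete null. Closed testing then needs only the F test at 5% for that intersection and each pair at 5%. Holm's thresholds (0.05/3 = 1.67%, 0.05/2 = 2.5%, 5%) never exceed 5%, so F followed by unadjusted pairs rejects every pair that the plan rejects.

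**2. Family-wise error, three groups of 20 (simulation, 200,000 runs).** Under the complete null it is 4.2% as written and 5.0% for F then unadjusted pairs. With one group far apart, F then unadjusted pairs gives about 5.0%.

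**3. Power for RTI v freehand, three groups.** In the first four rows RTI and IRI are equally better than freehand. Group sizes are in the order RTI/IRI/freehand. The last row used 100,000 runs, the others 200,000.

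| Scenario | As written | F then unadjusted pairs | Loss (points) |
|---|---|---|---|
| 20/20/20, d = 0.5 | 20.9% | 25.9% | 5.0 |
| 20/20/20, d = 0.8 | 56.0% | 63.9% | 7.9 |
| 20/20/20, d = 1.0 | 78.7% | 84.6% | 5.9 |
| 20/30/30, d = 0.8 | 66.9% | 75.4% | 8.5 |
| 20/20/20, d = 0.8, IRI midway | 53.3% | 57.3% | 4.0 |
| 20/20/20, RTI 0.8 and IRI 1.5 SD better than freehand | 65.1% | 70.1% | 5.0 |

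Hand check of Holm's first step, normal approximation: d × √(n/2) = 0.8 × √10 = 2.530. At 1.67% two-sided the critical value is 2.394, so power is Φ(0.136) = 55.4%, close to the simulated 56.0%.

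**4. Which layer costs the power.** In the d = 0.8 row, Holm without the gate gives 56.1% against 56.0% with it. With IRI midway it is 53.8% against 53.3%. Added to Holm, the gate costs at most about half a point.

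**5. Four groups.** A significant F no longer limits the true pairwise nulls to one, because three groups may be equal and one different. For F then unadjusted pairs:

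- Three groups equal, one far apart: family-wise error 12.2%. Three independent 5% tests would give 1 − 0.95³ = 14.3%; the pair tests are correlated, so the figure is lower. Holm brings it to 4.4%.
- Two equal pairs far apart: 9.8%, in line with 1 − 0.95² = 9.75%.
- Five groups (four equal, one far apart): 20.1%.

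**6. A sharper procedure for four groups.** The number of true pairwise nulls among four groups can only be 6, 3, 2, 1 or 0. After a significant F, at most 3 need protection. Shaffer's step-down thresholds are then 1.67% for the first four steps, 2.5% and 5%. Holm's are 0.83%, 1.0%, 1.25%, 1.67%, 2.5% and 5%. No Shaffer threshold is below Holm's, so everything that Holm rejects is also rejected. With four groups of 20 and all three guided technologies 0.8 SD better than freehand, power for RTI v freehand is 45.9% as written and 51.5% with gated Shaffer (100,000 runs). The family-wise error of gated Shaffer was at most 4.9%.

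**The case against.** The strongest reply is that the plan is valid, that Holm is a respectable default, and that it is necessary under the four or five groups named elsewhere in the document. All of that stands. Three stronger readings that someone might infer do not.

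- **The stacking is a double penalty.** Step 4 shows that one layer, Holm, accounts for nearly all of the loss.
- **Holm gives no needed error control.** That is true only for three groups. With the four of the first outcome, dropping it would let the family-wise error reach about 12%.
- **All-pairs testing is wrong because IRI v freehand is already answered.** The document does say that "the objective data of post-operative implant position has proven the PSI and IRI technology to be better than control groups". But the first outcome compares all the technologies, and the caption of Figure 2 calls the IRI data preliminary. Holm is also step-down: once IRI v freehand is rejected, the two RTI contrasts are tested at 2.5% and 5%, exactly as in a family of RTI contrasts only. With three groups of 20, limiting the family to RTI contrasts gains about 3 points when RTI equals IRI (59% v 56%) and none when IRI v freehand is overwhelming (65.0% both ways). The gain grows as IRI falls short of RTI. It reaches about 8 points (64% v 56%) if IRI is no better than freehand, which is at odds with the document's own account.

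It may also be said that Data Sheets lists at least five deviation measures (three positions, version, inclination) with no adjustment across them, which would give 1 − 0.95⁵ = 22.6% if they were independent, so this is no place to loosen control. That gap is real but separate: the change proposed here keeps 5% across the pairs within each measure.

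**Conclusion.** The point holds as one of efficiency, not of validity. For exactly three groups Holm after the F test is surplus. It costs about 5 to 8 points of power for RTI v freehand with 20 per group when RTI and IRI are equally better than freehand, and 4 to 8.5 points across all the scenarios tabulated. For four or more groups some correction is needed, but a sharper one than Holm is available, worth about 5 to 6 points in the four-group case.

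The closed-testing argument needs only that the F test and each pair test are valid at 5%. The sizes rest on assumed effects, comparator numbers, equal SD and normal data. The surgeon random effect in the planned model was not simulated; it would change the power figures but not the logic.

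**What to change.** 1. Settle the list of groups in Statistical Methods so that it agrees with the first outcome and the design text.
2. If exactly three groups are analysed, keep the 5% F test, follow it with unadjusted 5% pair tests, and state that closed testing justifies this.
3. If four or more are analysed, keep the gate and replace Holm by Shaffer's or another logically constrained step-down procedure, with its thresholds written out for that number of groups.
4. Optionally, name the RTI contrasts as the tested family and report the other pairs descriptively. This is a trade-off, since those pairs belong to the first outcome and would no longer be formally tested here.

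Items 1 to 3 cost a few sentences and no patients. All pairs remain tested, and the family-wise error stays at 5% within each measure. The change should be made before any RTI deviations are compared.
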